8.1.2.1 Immunogenicity Assessments Related to Fluzone High-Dose Quadrivalent Administration

Immunogenicity will be evaluated in all participants from the 3 study intervention groups using samples taken before vaccination and 21 days after Fluzone High-Dose Quadrivalent administration (21 [+3] days after V01) using the HAI test.

Test serum samples and quality control sera (sheep, ferret, and/or human sera) are incubated with Sigma Type III neuraminidase from *Vibrio cholerae* to eliminate non-specific inhibitors. Adsorption of spontaneous anti-species agglutinins is then performed by incubating the test serum samples and quality control sera with a red blood cell (RBC) suspension. Following this, the mixtures are centrifuged and the supernatants containing the treated sera are collected for testing. Ten two-fold dilutions (starting at 1:10) of the treated test serum samples and quality control sera are incubated with a previously titrated influenza antigen at a concentration of 4 hemagglutination units (HAU)/25 µL. Influenza antigen is not added to the serum control wells containing only serum and RBCs. The mixture is then incubated, and an RBC suspension is added. Following incubation, the results are read. The endpoint of the assay is the highest serum dilution in which complete inhibition of hemagglutination occurred. Each serum sample is titrated in two independent assay runs, and the 2 values, which cannot differ by more than 1 two-fold dilution, are reported. The GMT between the 2 values is calculated at the time of statistical analysis. The lower limit of quantitation (LLOQ) is set at the lowest dilution used in the assay, 1:10. Titers below this level are reported as < 10 (1/dil). If the highest / last serum dilution used in the assay

exhibits complete inhibition of hemagglutination, the serum Ab titer will be reported as ≥ 10240 (1/dil).

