8.1.2.2 Immunogenicity Assessments Related to Moderna COVID-19 Vaccine Administration

Human SARS-CoV-2 pre-Spike IgG ELISA

The human SARS-CoV-2 Pre-Spike IgG ELISA is an indirect ELISA which is based on the antibody/antigen interactions. This ELISA allows for the detection of SARS-CoV-2 Pre-Spike specific IgG antibodies in human serum samples and will be performed on all participants from the 3 study intervention groups.

Purified SARS-CoV-2 Pre-Spike Antigen is adsorbed to the wells of a microplate. Diluted serum samples (test samples, standard, and quality controls) are added in the wells. Anti-SARS-CoV-2 Pre-Spike antibodies, if present in the serum samples, bind to the immobilized SARS-CoV-2 Pre-Spike antigen. Unbound sample is then washed from the wells, and enzyme-conjugated anti-human IgG is added. The anti-human IgG enzyme conjugate binds to the antigen-antibody complex. Excess conjugate is washed away, and a specific colorimetric substrate is added. Bound enzyme catalyzes a hydrolytic reaction, which causes color development. After the established time period, the reaction is stopped. The intensity of the generated color is proportional to the amount of anti-SARS-CoV-2 Pre-Spike antibodies bound to the wells. The results are read on a spectrophotometer (ELISA plate reader). A reference standard on each tested plate is used to quantify antibodies against SARS-CoV-2 Pre-Spike in the sample according to the unit assigned by the standard (ELU/mL). At the time of the statistical analysis of the results, the following formula will be used for converting the concentration units from ELU/mL to BAU/mL:

$$\text{Result (BAU/mL)} = \text{Result (ELU/mL)} / 7.9815$$

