9.2 Sample Size Determination

The study will enroll approximately 300 participants 65 years of age or older: approximately 100 participants will be concomitantly administered of Fluzone High-Dose Quadrivalent vaccine and Moderna COVID-19 Vaccine (Group 1), approximately 100 participants will be administered Fluzone High-Dose Quadrivalent vaccine alone (Group 2), and approximately 100 participants will be administered Moderna COVID-19 Vaccine alone (Group 3).

No study power calculation was conducted for this study. Assuming a drop-out rate of 5%, a total of 95 evaluable subjects per study group is anticipated.

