3.3 Populations for Analyses

For the purposes of analysis, the following analysis sets are defined:

Participant Analysis Set	Description
Randomized	All participants that have a randomization number
Safety Analysis Set (SafAS)	Participants who received at least 1 dose of study vaccine. All participants will have their safety analyzed according to the vaccine they actually received and study intervention group. Safety data recorded for a vaccine received out of the protocol design will be excluded from the analysis (and listed separately).
Immunogenicity analysis set (IAS)	Subset of randomized participants who received at least 1 dose of study vaccine. Participants will be analyzed according to the vaccine they actually received and study intervention group.

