3.4.2 Safety Endpoints

The SafAS will be used. Safety will be assessed in all 3 study groups, however the assessment of the safety of the co-administration with regards to single administration will focus on groups 1 and 3, as influenza vaccine is expected to be less reactogenic.

Safety endpoints will be summarized, with 95% CI for the main endpoints, by actual study group. Injection site reactions will be summarized by actual study group and vaccine received; for subjects having received the 2 concomitant administrations, injections site reactions will be assigned to one of the 2 vaccines according to the side of vaccination/reaction.

In terms of contents, solicited reactions will be presented by time to onset, maximum severity, number of days of occurrence and action taken; unsolicited AEs will be presented by causal relationship, time of onset, maximum severity and duration; SAEs will be presented by causal relationship, seriousness and outcome.

Subgroup analyses will also be performed as complementary analyses; in particular, the main safety endpoints will be described according to gender and age group, as appropriate according to number of participants in the respective subgroups.

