3.4.3 Immunogenicity Endpoints

The IAS will be used. Immunogenicity endpoints will be summarized with 95% CI by actual study group and vaccine received, for each timepoint. Cumulative distribution frequencies will also be provided to support that concomitant vaccine administration does not interfere with the assay readout, particularly at the extremes of high and low titer results.

In addition, the ratios of post-vaccination GMTs between concomitant and single injections will be presented for the five antigens with 2-sided 95% CIs. A baseline adjustment will be applied using an ANCOVA model of the D22 log10 titer/concentration with vaccine group and D01 log10 titer as factor and covariate, respectively.

Subgroup analyses will also be performed as complementary analyses; in particular, immunogenicity will be described according to serostatus at baseline (pre-vaccination < or >= to LLOQ), previous influenza vaccination, gender and age group, as appropriate according to number of participants in the respective subgroups.

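### Does leaving the arms of the GMT-ratio ANCOVA unnamed in SAP 3.4.3 put the five confidence intervals at risk?

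*SAP*

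**What the plan says.** SAP 3.4.3 (Immunogenicity Endpoints) uses the immunogenicity analysis set and states that "the ratios of post-vaccination GMTs between concomitant and single injections will be presented for the five antigens with 2-sided 95% CIs". The baseline-adjusted version comes from an "ANCOVA model of the D22 log10 titer/concentration with vaccine group and D01 log10 titer as factor and covariate". Neither sentence lists arms, and the factor, vaccine group, is not defined. Protocol 9.4.3 announces the same ratios without a model.

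Four other places bear on the reading:

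- SAP 3.3 defines the immunogenicity set as "Subset of randomized participants who received at least 1 dose of study vaccine", so it contains all three groups, analysed by the vaccine actually received.
- Protocol 8.1.2.1 says of HAI: "Immunogenicity will be evaluated in all participants from the 3 study intervention groups using samples taken before vaccination". Protocol 8.1.2.2 says that the anti-S ELISA "will be performed on all participants from the 3 study intervention groups".
- SAP Table 2.1 times the day-22 HAI endpoint from the Fluzone injection and the day-22 anti-S endpoint from the Moderna injection.
- SAP 3.4.2, on safety, does name arms: "the assessment of the safety of the co-administration with regards to single administration will focus on groups 1 and 3".

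No hypothesis is tested (SAP 3.1) and no power calculation was made (Protocol 9.2).

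**The concern.** For each antigen one arm did not receive it before day 22: Group 3 for the four HAI strains and Group 2 for anti-S IgG. In that arm the day-22 value should sit close to the day-1 value. Its slope on baseline would then be near 1 and its scatter probably small. In the two arms given the antigen, the slope is likely to be flatter and the scatter larger.

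If all three arms enter one ANCOVA with a common slope and a common residual variance, two opposing errors arise. The quiet third arm lowers the pooled variance and narrows the CI. The forced common slope adds lack of fit and widens it.

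These ratios are the only planned between-group immunogenicity estimates, so their CIs are what a reader will use to judge interference. Two analysts working from the same text could report different intervals for all five antigens, and an interval that is too narrow would exclude 1 more than 5% of the time when there is no interference.

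**Working it through.** **Inputs.** From the documents: three arms at 1:1:1, two-sided 95% CIs, and "a total of 95 evaluable subjects per study group is anticipated" (100 × (1 − 0.05) = 95, which reproduces). The documents give no SD and no slope. The following are therefore assumptions on the log10 scale, with a true ratio of 1: slope b = 0.1 to 0.7 and residual SD sv = 0.25 to 0.50 in the two arms given the antigen; slope 1 and residual SD su = 0.08 to 0.25 in the third arm; baseline SD sb = 0.3 to 0.6.

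**Formulas.** With equal arms, the common slope in a three-arm fit is (2b + 1)/3. It misses the true slope by (1 − b)/3 in each vaccinated arm and by 2(1 − b)/3 in the third arm. Hence:

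- pooled residual variance, three arms: V3 = (2sv² + su²)/3 + (2/9)·sb²·(1 − b)²
- variance that actually drives the three-arm contrast: VT = sv² + sb²·(1 − b)²/9
- half-width, two arms: 1.973 × sv × √(2/95); three arms: 1.968 × √V3 × √(2/95)
- the three-arm CI is narrower, apart from the small difference in t, only if sb²(1 − b)² < 1.5(sv² − su²)

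**A narrow case** (b = 0.7, sv = 0.42, su = 0.12, sb = 0.5).

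- V3 = (0.3528 + 0.0144)/3 + (2/9)(0.25)(0.09) = 0.1224 + 0.0050 = 0.1274, against sv² = 0.1764.
- Half-widths are 0.102 (three arms) and 0.120 (two arms), a ratio of 0.85. As fold factors they are 1.265 and 1.32, so around a ratio of 1 the CI runs 0.79 to 1.27 instead of 0.76 to 1.32.
- VT = 0.1764 + 0.0025 = 0.1789. Coverage is P(|Z| < 1.968 × √(0.1274/0.1789)) = P(|Z| < 1.66) = 90.3%, which matches the simulation.

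**A wide case** (b = 0.1, sv = 0.25, su = 0.15, sb = 0.5).

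- V3 = 0.0492 + 0.0450 = 0.0942, against 0.0625.
- Half-widths are 0.0876 and 0.0716, a ratio of 1.22. Fold factors are 1.224 and 1.179.
- VT = 0.0850, so coverage is about 96.2%.

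**Baseline SD can set the sign.** With b = 0.3, sv = 0.25 and su = 0.15, √(V3/sv²) is 0.97 at sb = 0.3 and 1.19 at sb = 0.6.

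**Full grid.** Simulating 4,000 trials at each of 256 combinations gives a three-arm to two-arm width ratio of 0.824 to 1.424. Coverage is 88.6% to 97.5% for three arms and 94.1% to 96.0% for two. The mean error of the log10 ratio is at most 0.003 in either model. A separate simulation over other settings (6,000 runs each, including a third-arm SD of up to 0.5) gave width ratios of 0.85 to 1.32 and two-arm coverage of 94.6% to 95.5%.

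**Dependence on the fixed slope of 1.** At the widest corner (b = 0.1, sv = su = 0.25, sb = 0.6), √(V3/sv²) is 1.43. Replacing the third-arm slope of 1 by 0.8 gives √(0.1017/0.0625) = 1.28, and 0.7 gives √(0.0913/0.0625) = 1.21. Assay error in the day-1 value would push the slope in that direction.

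**Which model does the text call for?** All of the above matters only if the three-arm model is what the SAP asks for. The requested quantity is a ratio of post-vaccination values, concomitant over single injection.

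| Antigen | Concomitant arm | Single-injection arm | Arm with no injection of that antigen before day 22 |
|---|---|---|---|
| Four HAI strains | Group 1 | Group 2 | Group 3 |
| Anti-S IgG | Group 1 | Group 3 | Group 2 |

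Each row has one numerator and one denominator. Because SAP Table 2.1 times day 22 from injection of the relevant vaccine, the last column has no post-vaccination value in that sense. Group 3's optional influenza dose comes only after all Visit 2 procedures (Protocol 2.3.2), so it does not alter this.

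**The case for a change.** The best case for a change is that the wording fixes the contrast but not the data used to fit the model. A three-level factor with a Group 1 versus Group 2 contrast would also satisfy the sentence, the analysis set and both assays supply the data for it, and Protocol 9.4 leaves the technical detail to the SAP. The study is open-label, so an unstated choice could be made with results in view, and one sentence would remove the doubt at almost no cost.

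Part of this stands. The arms are not listed, the three-arm fit is not excluded, and the variance algebra is sound.

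Two parts carry less weight. The comparison with SAP 3.4.2 does not show an oversight: safety has two possible single-injection comparators, so the SAP had to say which one it would focus on, and it gave its reason. For each antigen there is only one, so naming it adds little. The argument that a literal reading leads to three arms also fails. The sections on the immunogenicity set and the assays say who is sampled and tested, not who enters each model, and no sentence prescribes three arms.

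**Conclusion.** No change is needed. The SAP states no rule that yields a wrong interval. It leaves out a detail that the requested ratio and the endpoint timing supply: a separate two-arm ANCOVA per antigen, Groups 1 and 2 for the HAI strains and Groups 1 and 3 for anti-S IgG.

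The possible harm, a CI about 18% narrower to 42% wider, arises only if an analyst chooses the less natural model. Its size rests wholly on assumed SDs and slopes, and the wide end depends on a third-arm slope of exactly 1. The narrow end does not depend on that slope in the same way and would be a real loss of coverage if the three-arm model were used. Even then the ratio stays unbiased, the per-arm GMT intervals are untouched, and no test, margin or success rule turns on the result.

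The near-nominal two-arm coverage was itself shown for normal data with equal slopes and variances in the two vaccinated arms, without the substitution of values beyond the quantification limits (SAP 4.2.3.1).

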3.4.4 Handling of Missing Data and Outliers

3.4.4.1 Safety

Generally, no replacement will be done for Safety Missing Data and Outliers.

3.4.4.1.1 Immediate

For unsolicited systemic AEs, a missing response to the “Immediate” field is assumed to have occurred after the 30-minute surveillance period and will not be imputed.

3.4.4.1.2 Causal Relationship

By convention, all events reported at the injection site (either solicited or unsolicited) will be considered as related to the administered product and then referred to as reactions. In a same way, all solicited systemic events pre-listed in the CRF are also considered as related to vaccination and will be considered as reactions.

- For unsolicited systemic AE, missing relationship will be considered as related to study vaccine(s) at the time of analysis.
- The missing relationship to study procedures for SAEs will not be imputed.

3.4.4.1.3 Intensity

For solicited reactions, missing intensities will be handled as described in Section 4.2.1.1.1. For unsolicited AEs, missing intensities will remain missing and will not be imputed.

3.4.4.1.4 Start Date and End Date

Missing or partially missing start dates or end dates for unsolicited AEs (including SAEs) will remain missing and not be imputed. If the start date is missing or partially missing, the time of onset will be considered missing. If either the start date or end date is missing or partially missing, the duration will be considered missing.

Missing or partially missing end dates for ongoing solicited AEs will remain missing and not be imputed.

3.4.4.1.5 Action Taken

Missing actions taken will remain missing and not be imputed.

3.4.4.2 Immunogenicity

No imputation of missing values and no search for outliers will be performed. LLOQ and ULOQ management will be performed as described in Section 4.2.3.1.

3.5 Interim Analysis

The statistical analysis will be performed in two or three steps, depending on the availability of immunogenicity data: the safety objectives up to D22 will be analyzed first and the immunogenicity objectives will be analyzed in a second step, after immunogenicity data have been released. No impact is expected on immunogenicity results as the conduct of

immunogenicity assays will remain blinded. At last, the final analysis will be performed when safety data up to D181 is released.

3.6 Data Monitoring Committee (DMC)

Not applicable

4 Complementary Information on Assessment Methods

Study assessments and procedures are detailed in Section 8 of the protocol. This section focusses on complementary/additional information not detailed in the protocol.

4.1 Complementary Information for Endpoints Assessment Method

Not applicable. **Complementary Information on Derived Endpoints: Calculation Methods**

4.2.1 Safety

4.2.1.1 Solicited Reactions

4.2.1.1.1 Daily Intensity

All daily records for solicited reactions will be derived into daily intensity according to the following classification: None, Grade 1, Grade 2, Grade 3, or Missing (Unknown).

For the derivation of daily intensities, the following sequential steps will be applied:

- 1) Solicited reactions (except Fever/Pyrexia) with CRF presence recorded as “No” and with all daily records missing (Unknown) then all daily intensities will be derived as None.
- 2) For non-measurable solicited reactions, daily intensities will correspond to daily records reported in the clinical database. For measurable solicited reactions the daily measurements reported in the clinical database will be converted based upon the intensity scales defined in the protocol; this assumes a reaction that is too large to measure (non-measurable, “NM”) is Grade 3. Note the intensity could be considered “None” (not a reaction) in the analysis despite being considered a reaction by the investigator (e.g., swelling measurement > 0 mm but < 25 mm in adults).

Note: The maximum intensity on the ongoing period is derived from the record of the maximum intensity/measurement after the end of the solicited period following the rule described above.

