8.3.2 Method of Detecting AEs and SAEs

Individual diary cards, specifically designed for this study by the Sponsor and provided to the study sites, will be given to study participants for the recording of daily safety information. These diary cards will include pre-listed terms and intensity scales as well as areas for free text to capture additional safety information or other relevant details. Participants will also be provided with rulers for measuring the size of injection site reactions, and with standard digital thermometers for measuring daily temperatures. To ensure consistency of reporting, the study sites will instruct participants on how to correctly use these tools.

At specified intervals, the Investigator or a designee will interview the participants to collect the information recorded in the diary card, and will attempt to clarify anything that is incomplete or unclear. All clinical study information gathered by the study site will be reported electronically by the Investigator or designee using a web-based CRF. Any information that was not documented in the diary card will first be captured in the source document and then reported electronically.

The 6-month follow-up will be done by interviewing participants over the telephone to capture SAEs, AESIs, and MAAEs if applicable.

Care will be taken not to introduce bias when detecting AEs and/or SAEs. Open-ended and non-leading verbal questioning of the participant is the preferred method to inquire about AE occurrences.

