4.2.1.1.3 Presence

Presence is derived from the maximum overall intensity over the time period considered:

- None: No presence

- Grade 1, Grade 2, or Grade 3: Presence
- Missing or Unknown: Missing presence

Participants with at least one non-missing presence for a specific endpoint will be included in the analysis. Conversely, those without a non-missing presence will not be included in the analysis of the endpoint.

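### For solicited reactions graded by activity, a CRF 'No' without any daily record is kept as a non-reaction but a CRF 'Yes' without any daily record is lost, which can only lower the rate

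*SAP*

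**What the plan says.** SAP 4.2.1.1.1 derives daily intensities in two sequential steps.

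- Step 1 applies to "Solicited reactions (except Fever/Pyrexia) with CRF presence recorded as" No. Such a reaction "with all daily records missing (Unknown) then all daily intensities will be derived as None".
- Step 2 covers everything else from the daily data alone: "For non-measurable solicited reactions, daily intensities will correspond to daily records reported in the clinical database". Measurable reactions are converted from the daily measurement with the protocol's size scale.

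SAP 4.2.1.1.2 takes the maximum of the daily intensities. SAP 4.2.1.1.3 turns None into no presence, Grades 1 to 3 into presence, and otherwise applies "Missing or Unknown: Missing presence". It then sets the denominator: "those without a non-missing presence will not be included in the analysis of the endpoint".

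No other section changes this. SAP 3.4.4.1 says that safety data are in general not replaced, and SAP 3.4.4.1.3 points back: "For solicited reactions, missing intensities will be handled as described in Section 4.2.1.1.1".

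Protocol Table 10.1 gives size scales for four injection site reactions (erythema, swelling, induration, bruising). I read the other three (pain, axillary swelling, axillary tenderness) as graded by effect on activity. In Protocol Table 10.2 every systemic reaction except fever is graded by activity.

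**The concern.** The same CRF field is accepted when it says No and has no effect when it says Yes. A reported non-reaction counts; a reported reaction without any daily grade disappears from both numerator and denominator. For activity-graded reactions that is exclusion on the outcome.

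The situation can arise. Step 1 itself presupposes a presence answer without daily records, and Protocol 8.3.2 provides that "Any information that was not documented in the diary card will first be captured in the source document and then reported electronically". A participant who lost the diary but recalls a headache at interview could have a Yes and no daily grades.

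The rule is also out of line with the SAP's handling of unsolicited events. There an event needs only a verbatim term and an intensity other than Grade 0 (4.2.1.2.1), and a missing intensity simply stays missing (3.4.4.1.3). In 4.2.2.6, unsolicited events causing discontinuation count with intensity missing, while solicited ones need at least Grade 1.

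Solicited reactions within 7 days are a listed safety endpoint, and SAP 3.4.2 judges co-administration mainly on Groups 1 and 3.

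**Working it through.** **Scale.** Protocol 9.2 expects 100 × (1 − 0.05) = 95 evaluable participants per group, which reproduces. It is used here only as N; the documents give no reaction rates and no count of missing diaries, so all counts below are assumed.

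**Following one participant through the rules (activity-graded reaction, all daily records missing).**

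| CRF presence | Daily intensity | Maximum | Presence | In the denominator? |
|---|---|---|---|---|
| No | None (step 1) | None | No presence | Yes, as a non-reactor |
| Yes | Missing (step 2) | Missing | Missing | No |

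The second row is an inference from step 2 and 4.2.1.1.3; no sentence states it. It needs all daily records for that reaction to be missing. I read one graded day as enough to keep the participant, because the maximum is then defined. The exclusion is per endpoint.

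**Direction.** Let a be the participants with a graded reaction and y those with Yes and no daily record.

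- SAP rate = a/(N − y).
- Rate with Yes counted = (a + y)/N.
- Difference = (a + y)/N − a/(N − y) = y(N − a − y) / [N(N − y)].

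This is never negative, since a + y cannot exceed N. A check over all a and y at N = 95 found no case where the SAP rate was higher.

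**Size, N = 95 (shift in percentage points).**

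| Rate with Yes counted | y = 1 | y = 2 | y = 5 |
|---|---|---|---|
| 10/95 = 10.5% | 9/94 = 9.6% (−0.95) | 8/93 = 8.6% (−1.92) | 5/90 = 5.6% (−4.97) |
| 30/95 = 31.6% | 29/94 = 30.9% (−0.73) | 28/93 = 30.1% (−1.47) | 25/90 = 27.8% (−3.80) |
| 60/95 = 63.2% | 59/94 = 62.8% (−0.39) | 58/93 = 62.4% (−0.79) | 55/90 = 61.1% (−2.05) |
| 80/95 = 84.2% | 79/94 = 84.0% (−0.17) | 78/93 = 83.9% (−0.34) | 75/90 = 83.3% (−0.88) |

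For comparison, the Clopper-Pearson 95% interval for 30/95 is 22.4% to 41.9%.

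**Size-graded reactions.** If k of the y unmeasured Yes cases truly reached 25 mm, the rate to compare is (a + k)/N. The SAP rate is too low only if k/y exceeds a/(N − y). With a = 20 and y = 5 the SAP rate is 20/90 = 22.2%:

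- k = 0: 20/95 = 21.1%, SAP too high by 1.2.
- k = 1: 21/95 = 22.1%, SAP too high by 0.1.
- k = 5: 25/95 = 26.3%, SAP too low by 4.1.

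**Fever.** Step 1 does not apply, so No and Yes without any temperature are both excluded.

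- 8 fevers, five No cases lost: 8/90 = 8.9% against 8/95 = 8.4% (+0.5).
- 8 recorded fevers, two Yes cases lost: 8/93 = 8.6% against 10/95 = 10.5% (−1.9).

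**Difference between groups.** Suppose a fraction m of participants in each group has a presence answer but no daily records, unrelated to reacting, and the true rate is p. The reported rate is p(1 − m)/[(1 − m) + m(1 − p)].

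- 70% versus 50% (true gap 20): m = 5% gives 68.91 − 48.72 = 20.19; m = 10% gives 67.74 − 47.37 = 20.37. The gap widens.
- 50% versus 30% (true gap 20): m = 10% gives 47.37 − 27.84 = 19.53. The gap narrows.

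**The case against.** A reader might infer more than the SAP supports, and four objections limit the point.

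- **All solicited rates biased downward.** Not so. Fever is expressly outside step 1. For size-graded reactions, ignoring an unmeasured Yes has a rationale: No implies nothing to measure, but Yes does not imply 25 mm. The SAP says that an investigator-reported reaction below that size is analysed as None, and in 4.2.1.1.7 it lets the measurement override the investigator's ongoing flag. This stands, so the directional claim is confined to activity-graded reactions.
- **A smaller Group 1 versus Group 3 contrast.** The arithmetic above shows that the gap can widen or narrow. No direction can be claimed.
- **Frequency.** The documents give no count, and the protocol works against such cases: a telephone contact at D08, instruction on the diary tools, and an interview to clarify incomplete entries. The expected 5% drop-out is a different quantity. This stands; the number is probably small. The CRF is not among the documents, so how its presence field is completed is also unknown.
- **Convention.** The study is descriptive, tests no hypothesis and in general replaces no missing safety data. But step 1 already fills in missing daily records from the presence entry, so using that entry in one direction only is not a neutral no-replacement rule. This objection limits the consequence and does not remove the asymmetry.

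**Conclusion.** The point holds for solicited reactions graded by activity: injection site pain, axillary swelling and tenderness, and all systemic reactions except fever. For these, the SAP as written can only understate the rate, or leave it unchanged if no such case occurs.

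The conclusion rests on three assumptions: the CRF presence entry is correct, Yes can be recorded without any daily record, and step 2 is applied literally. With one or two cases among 95 per group the shift is about 0.2 to 2 points; five cases would give up to 5 points where the reaction is uncommon. It is a small effect, but the rule removes reported reactions from a safety endpoint.

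**What to change.** Add a step to SAP 4.2.1.1.1, with a matching line in 4.2.1.1.3:

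- **Activity-graded reactions (not fever):** CRF Yes with all daily records missing counts as Presence with maximum intensity Missing. The participant enters the numerator and denominator of the any-reaction row, and the severity table gains a Missing line.
- **Size-graded reactions (erythema, swelling, induration, bruising):** keep presence Missing in the main table, report by group the number of CRF Yes entries without any measurement, and give a sensitivity count that includes them.
- **Fever:** unchanged.

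The cost is a sentence or two in the SAP, a small programming change and one extra table line. If no such cases occur, no result changes. The any-reaction row would then rest partly on ungraded reports, which the Missing line makes visible.
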